4 STUDY DESIGN

4.1 DESIGN OVERVIEW

This is an open-label, Phase I, single arm study to evaluate the safety and feasibility of autologous volar fibroblasts to reprogram non-volar to KRT9-expressing volar epidermis in human participants.

We anticipate enrolling 20 patients with full accrual expected within six months for Phase One of the study. To complete Phase Two objectives, an additional 80 subjects will be enrolled. Thus, up to 100 patients may be consented in order to complete enrollment for both Phase One and Phase Two of the study. No part of this protocol will be considered routine care.

4.1.1 BLINDING/RANDOMIZATION

The clinicians will not be blinded, but the research staff who measure epidermal thickness and KRT9 levels will be blinded. It will be impossible to blind the clinicians since they will be injecting the cells versus vehicle. Although we could blind the clinicians to the identity of volar versus non-volar cells, it might be important to judge adverse events and will not impact on endpoint determination—primarily occurring in the laboratory. Another reason not to blind the clinicians is that this is a feasibility trial.

We will blind the research staff by labeling sites/biopsies with numbers (1, 2 or 3) rather than the identity of injected cells at that location. At the injection visit, the numbers are assigned as in the CRF (see Appendix V) with the corresponding identity of cells injected by the clinician. This injection form will not be available to research staff unless there is an adverse event when un-blinding will occur. Blinding will occur for research staff both during measurements of epidermal thickness/area by OCT as well as in the laboratory phase where the removed injection sites will be analyzed by histology and RT-PCR.

The subjects will also only be told the number of each site so that subjects will be blinded as well (See Appendix VI; injection diary).

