2 PRIMARY OBJECTIVE

1. To determine the safety and tolerability of the use autologous volar fibroblasts to reprogram non-volar to KRT9-expressing volar epidermis in human participants.

SECONDARY OBJECTIVES

1. To measure non-invasively for epidermal thickening in sites of injection of volar fibroblasts compared to both non-volar fibroblast injection and vehicle only injection
2. To measure for molecular changes in excised injected skin (for example increases in KRT9).
3. To describe persistence of epidermal thickening in sites of injection of volar fibroblasts over time.
4. To evaluate the safety and efficacy of an intermittent, serial dosing regimen of the autologous volar fibroblasts.
5. To evaluate the efficacy of superficial wounding with a curette at the injection sites.

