5.2.3 SUTURE REMOVAL VISIT (VISIT #2) (STUDY DAY 14 +/- 2 DAYS)

The participant will return to clinic for suture removal. At this study visit, the following will be obtained/performed:

- Vital signs including BP, pulse, and respirations
- Biopsy site/AE assessment
- Biopsy site suture removal

The participant will be given their graft administration visit appointment at this time.

5.2.4 GRAFT INJECTION VISIT PHASE ONE VISIT #3 (STUDY DAY 30 +/- 7 DAYS) OR PHASE TWO VISITS #3-6 (STUDY DAYS 30, 37, 42, 59)

The participant will return to the clinic on or near Day 30 for their graft injection.

Participants will have the following assessments done:

- History and limited physical examination
- Females of child bearing potential will have a urine pregnancy test done prior to administration of the investigational cells to ensure that they are not pregnant.
- Clinical photographs will be taken of each of these 3 sites before the investigational product is administered. These photographs will be used throughout the study to document changes in the skin as well as aid in location of the site at subsequent visits. Photograph files will be coded with the participant's unique identifier. The participant will not be identifiable from the clinical photographs.

Together with the study investigator, a site for injection of the subject's grown fibroblasts will be chosen. The injections will be placed by the investigator into the three sites mutually identified (e.g. the three injections will be placed on one of

the participant's buttocks, or non-buttocks area as above). The injection sites will be spaced at least 5 cm from the center of any neighbor and may be divided between left and right buttocks or non-buttocks area as above to ensure a lack of overlap.

Identification of injection sites to optimize future localization will occur through these steps:

- We will identify distances and angle from anatomical landmarks such as the sacroiliac joint.
- We will draw anatomical landmark maps with transparency paper used for projections. We will circle landmarks so that the transparency can be directly placed on the subjects buttocks or non-buttocks area as above in a repeatable orientation, and also identify injection sites.

To further enhance our ability to localize injection sites, we will use a small volume of ($x < 0.025$ ml) tattoo ink to mark areas of cellular injection:

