
If a subject refuses consent for the tattoo marker, but is otherwise willing to complete all other study procedures, then we can use the palpated sacral hiatus, and initiation of the gluteal cleft as 2nd and 3rd universal landmarks. In addition, we will maximize the use of individual landmarks such as nevi, seborrheic keratoses, scars and hemangiomas which are found on human skin. In previous studies that the PI has performed(1), he has used exactly this method for the injection of hyaluronic acid to identify sites months later and had universal success at identifying injection sites. Also, to enhance our ability to identify sites we will not limit injections to one side of the buttocks (or non-buttocks area as above) to enhance the available number of landmarks and ensure proper identification in subsequent visits after the injection. Finally, we will frequently also consult clinical photographs (photographed with rulers) of the injection site taken on the day of injection to optimize our ability to correctly map injection sites.

We will avoid injection into the skin above the ischial tuberosity to minimize discomfort and risks of ulcers

Phase One: Single Dose Injection

After numbing the participant with anesthesia described in Visit 2, two of the sites will be injected with 0.7-0.8 mls of media (5% DMSO, 6% hetastarch and 2.5% human serum albumin) containing 30-40 million autologous fibroblasts into a small area about 3-4mm injection area subepidermally at the level of the epidermis-

dermis junction. The third site will be injected with the same volume of media containing no autologous cells.

Phase Two: Intermittent Dosing Regimen

We do not propose to increase the total number of cells injected, but to inject fewer cells more often. At the PI's discretion, the subject may receive injections of the dosing regimen or injections of 10% DMSO.

Two of the three treated sites will receive cells. A total of 4 injections may maximally occur; the first will always include cells for these sites. The remaining 3 injections may include vehicle and up to 10% DMSO instead of cells administered within 30 days after injection of cellular product.

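### No chance rule is stated for which of the three skin sites receives volar cells, non-volar cells or vehicle, so a systematic link between content and position could bias the between-site thickness comparisons

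*Combined protocol and SAP*

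**What the plan says.** Secondary objective 1 (section 2) is a controlled comparison within each person: "To measure non-invasively for epidermal thickening in sites of injection of volar fibroblasts compared to both non-volar fibroblast injection and vehicle only injection".

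On who knows what, section 4.1.1 states: "The clinicians will not be blinded, but the research staff who measure epidermal thickness and KRT9 levels will be blinded". On the link between site number and content it says: "At the injection visit, the numbers are assigned as in the CRF (see Appendix V) with the corresponding identity of cells injected by the clinician". The form it refers to, Appendix V, has three blank rows and no pre-set assignment.

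On placement, section 5.2.4 says: "Together with the study investigator, a site for injection of the subject's grown fibroblasts will be chosen", and then: "The injections will be placed by the investigator into the three sites mutually identified". The spacing rule is: "The injection sites will be spaced at least 5 cm from the center of any neighbor and may be divided between left and right buttocks". Areas other than the buttocks are also allowed. Section 5.2.2 has the three sites identified and tattooed at the baseline visit, about 30 days before injection, although 5.2.4 also describes choosing at the injection visit.

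OCT appears in both schedules of evaluations only from the first monitoring visit onward. Section 9.2 specifies a Student's t-test of volar against non-volar thickness values at p < 0.05, and the same for KRT9 mRNA. It mentions neither baseline nor position.

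**The concern.** A difference in thickness between sites can be attributed to cell type only if cell type is unrelated to where on the body the site lies. Three positions at least 5 cm apart, possibly on different sides, may differ in native thickness. Without a chance rule, any regular practice, such as volar cells usually going to the same position, adds the native difference between positions to the volar effect, in the same direction in every participant.

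Nothing later in the plan would remove this. There is no pre-injection thickness to subtract and no position term in the test. Numbered labels stop the raters from favouring a product, but a blinded rater still measures a confounded site. If volar cells habitually carried the same number, the raters could also come to guess it.

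At stake is the interpretation of the thickness result, which is meant to inform later trials. Once the cells are injected, the allocation cannot be repaired.

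**Working it through.** **The plan's own figure.** Section 9.2 assumes a difference of 2, SD 0.5, alpha 0.06 and power 0.8, and concludes that 3 participants suffice. The standardised difference is 2/0.5 = 4. For a two-sided unpaired t-test the noncentrality is 4 × √(n/2). With n = 2 per group the power is 63%; with n = 3 (noncentrality 4.90, 4 degrees of freedom) it is 96%. So 3 reproduces. It says nothing about allocation.

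**What the bias equals.** Let the volar position be natively thicker than the comparison position by b, let there be no cell effect, and let volar cells go to the thicker position in a fraction q of participants. The expected volar-minus-control difference is q·b − (1 − q)·b = (2q − 1)·b. This is b if q = 1, half of b if q = 0.75, and 0 if q = 0.5. The number of participants does not enter, so enlarging the trial only makes the spurious difference easier to declare significant.

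**Size, as an illustration.** Inputs:
- n = 20 (Phase One, section 4.1).
- Per-site SD 0.5. Section 9.2 gives 0.5 for all samples and no units, so I treat it as the SD of the values at a site.
- Two-sided p < 0.05, counting only results in the volar-thicker direction.
- Assumed, because the documents give neither: b = 0.1, 0.2 or 0.3, and a correlation r between sites in the same person of 0 or 0.5.

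For a paired test the SD of the difference is 0.5 × √(2(1 − r)): 0.707 at r = 0 and 0.5 at r = 0.5. The noncentrality is b × √20 divided by that SD. At b = 0.2 it is 1.265 and 1.789, which gives 22% and 40%. For an unpaired test with r = 0 the noncentrality at b = 0.2 is 0.2/(0.5 × √(2/20)) = 1.265 on 38 degrees of freedom, which gives 23%. The unpaired results at r = 0.5 come from simulation (40,000 runs).

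False volar-thicker results with volar cells always in the thicker position:

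| b | Unpaired, r = 0.5 | Unpaired, r = 0 | Paired, r = 0 | Paired, r = 0.5 |
|---|---|---|---|---|
| 0.1 | 3% | 9% | 9% | 13% |
| 0.2 | 16% | 23% | 22% | 40% |
| 0.3 | 44% | 46% | 44% | 72% |

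With volar cells assigned to either of the two positions at random in each participant, the same simulation gives about 2.5% for the paired test. The unpaired test gives 2.5–3% at r = 0 and under 1% at r = 0.5, where it is conservative because it ignores the pairing.

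At b = 0.2 with q = 0.75 in place of 1, the rates fall to about 4–9% (unpaired) and 8–13% (paired). With fixed placement and n = 100, the most that may be consented over both phases, b = 0.2 gives 80–88% (unpaired) and 80–98% (paired).

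**Why a balanced permutation works.** Three contents over three positions give 3! = 6 orders. Across the six, every pair of contents occupies every pair of positions equally often in both directions, so the native differences cancel.

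**The case against.** The strongest reply is that this is an open-label Phase I feasibility study whose primary outcome is tolerability, with a more formal trial planned next (section 6.3.2), and that no habitual placement has been shown. Most of that is fair, and it limits the point in several ways.

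- *That the clinician chooses which product goes where.* A reader might infer this, but no sentence says so. Section 4.1.1 says that contents are recorded against numbers, not how they are matched to positions. Nor does the wording "The third site will be injected with the same volume of media containing no autologous cells" fix vehicle at position 3; third can simply mean the remaining site. What can be said is that no rule is stated. The study schemas that section 5.2.5 refers to are not reproduced in the text available here, and I assume that they contain none.
- *That every group comparison is compromised.* The documents do not support this. Tolerability is not a position contrast, and the Phase Two questions on schedule and wounding are not position contrasts as such. Section 3 calls KRT9 unique to volar skin, and all three sites are non-volar, so native position differences are an unlikely source of a KRT9 rise.
- *That the bias is known to be large.* It is not. The offsets are assumptions, and sites that vary between participants work against a consistent position effect. An offset of 0.2 is one tenth of the planned difference of 2 (0.2/2), so it could not imitate an effect of that size.
- *That the sites are fixed early.* Identifying them at baseline limits choosing a location to suit a product, but not matching product to location afterwards.

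Section 4.1.1 argues that unblinded clinicians will not affect the endpoints because these are determined mainly in the laboratory. That answers measurement bias, not allocation. Clinicians can stay unblinded and still follow a list.

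Two neighbouring problems would survive random allocation. Appendix VII puts the identity of the product on the excised-tissue tubes. And the early-removal test compares sites within one participant, where a native difference cannot average out.

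**Conclusion.** The point stands as a should-fix. The plan states no chance rule for allocating contents to sites and leaves placement and recording to the unblinded clinician. It has no pre-injection thickness measurement and no position term. A systematic link between content and position would therefore bias the thickness comparisons of secondary objective 1, by an amount that does not shrink with sample size.

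Whether such a link would arise, and how large the native differences are, cannot be known from the documents. Over the assumed offsets of 0.1 to 0.3 units with fully fixed placement at n = 20, a false volar-thicker result occurs in about 3–46% of trials with the unpaired test and about 9–72% with the paired one. Section 9.2 does not say that the test is paired, so the upper paired figures should not be read as the plan's error rate.

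**What to change.** In sections 4.1.1 and 5.2.4:

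1. Define and number positions 1 to 3 by the same anatomical convention in every participant, when the sites are marked at the baseline visit (or mapped, for those who decline the tattoo). Balancing over positions helps only if a position number means the same place in everyone.
2. Assign volar, non-volar and vehicle to the positions from a pre-generated random permutation per participant, balanced over the six orders and opened only after the sites are marked. Enter it on the Appendix V form.
3. Where possible, keep a participant's three sites in comparable skin of one body region. Left and right buttock should count as one region, so that the use of both sides for landmarks in 5.2.4 is kept.

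The cost is a short protocol edit and a one-page list, with no added visits, staff or procedures. The investigator gives up choosing which site gets which product. An OCT reading before injection at an existing visit would be a useful addition, at the cost of one more imaging session, but the fix does not depend on it.

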5.2.5 GRAFT MONITORING AND REMOVAL

Dependent upon participant response, as many as six monitoring visits will be conducted to evaluate skin thickness and adverse events (see study Schemas, page 3-4). As per the pre-IND discussion with FDA, persistence of any thickening response is of particular interest. In order to assess this, we will divide the subjects such that there will be 2 groups. The first portion will immediately have graft removal once skin thickness increases in order to assess the molecular features of induction of volar skin, and a 2nd portion of subjects will instead be followed for permanence of effect, and undergo graft removal at the conclusion of 10 months of the study.

The method of dividing the subjects will be as follows. At all monitoring visits all injected sites on all subjects will be measured for epidermal thickness by non-invasive confocal imaging or through the non-invasive measurement of skin induration (as long as those injected sites have not been removed through biopsy). The first three subjects who demonstrate a statistically significant increase of measured epidermal thickness on the volar fibroblast injected side will have their grafts removed during the follow-up visit that the increased thickness determined to be statistically significant.

The means of calculating an increase in epidermal thickness of the volar fibroblast injected site will be through a t-test statistical analysis of 3 sequential readings (within a visit) from the three injection sites (no fibroblasts, non-volar fibroblasts, and volar fibroblasts). For a subject to be designated as an “early graft removal”, he/she should have a statistically significantly elevated epidermal thickness in the volar injected site but not the non-volar or vehicle-only injected sites.

If no subjects show an increase, then all subjects will be followed for epidermal thickness till the end of the study and undergo graft removal at the end of the 10 months. If fewer than 3 subjects are identified before the end of the study to have an increase, then the remainder will undergo graft removal at the end of the study. If more than 3 subjects are identified, then those remaining subjects will be

followed through Visit 8 and undergo graft removal at the end of the 10 month period..

“Early Graft Removal” subjects will skip all remaining graft monitoring visits and instead go directly to suture removal visit.

All subjects will have at least one monitoring visit.

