6. RISKS/BENEFITS

6.1 RISKS

6.1.1 AUTOLOGOUS VOLAR FIBROBLASTS

We expect to remove the injected cells, but cellular injections have been rarely associated with mild redness, bruising, swelling, pain, bumps, irritation and itch at the injection site in less than 10% of participants. Injection site reactions may occur including pain, bruising, swelling, erythema, pigmentation changes, induration.

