7. ADVERSE EVENT COLLECTION AND REPORTING REQUIREMENTS

7.1. DEFINITIONS

7.1.1. ADVERSE EVENT (AE)

An adverse event (AE) will be defined as an unusual and undesirable symptom or sign that occurs in participants during the clinical study. Adverse events include those clinically significant laboratory values and test results, concomitant illness, accident, medical occurrence or worsening of existing medical condition that emerge during study participation.

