7.2. ADVERSE EVENT GRADING

Adverse events will be identified and graded using the schema described below. The investigator will evaluate the severity of any adverse event using the following definitions:

- *Mild* - event may be noticeable to participant; does not influence daily activities; usually does not require intervention.
- *Moderate* - event may be of sufficient severity to make participant uncomfortable; performance of daily activities may be influenced; intervention may be needed.
- *Severe* - event may cause severe discomfort; usually interferes with daily activities; participant may not be able to continue in the study; treatment or other intervention usually needed.

AEs graded as ‘severe’ which are possibly, probably, or definitely attributable to the use of the investigational drug will be recorded and monitored until the event has resolved to meet the definition of ‘mild’. All participants will receive care for all adverse events according to good clinical practice as per the standard of care at Johns Hopkins.

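### Section 4.1.1 opens the injection code to the blinded assessors for any adverse event, early graft removal can hint at the code, and Appendix VII prints it on every excised tube

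*Combined protocol and SAP*

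**What the plan says.** **The blind.** Section 4.1.1 leaves the clinicians unblinded, partly because cell identity may matter when they judge adverse events. The research staff who measure thickness and KRT9 know the sites only as 1, 2 or 3. The scope is explicit: "Blinding will occur for research staff both during measurements of epidermal thickness/area by OCT as well as in the laboratory phase".

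**The exception.** The same section continues: "This injection form will not be available to research staff unless there is an adverse event when un-blinding will occur".

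**What counts as an adverse event.** Section 7.1.1 defines it as "an unusual and undesirable symptom or sign that occurs in participants during the clinical study". The lowest grade in section 7.2 is described as: "event may be noticeable to participant; does not influence daily activities; usually does not require intervention". Section 6.1.1 reports, from experience with cellular injections, "mild redness, bruising, swelling, pain, bumps, irritation and itch at the injection site in less than 10% of participants". It then lists further possible reactions, including induration, without a frequency.

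**Early removal.** Sections 5.2.5 and 9.2 allow early graft removal for three subjects, on the condition that "he/she should have a statistically significantly elevated epidermal thickness in the volar injected site but not the non-volar or vehicle-only injected sites". Removed subjects have no further monitoring visits.

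**Tube labels.** Appendix VII, on the final excision of the three injected sites, has each tube carry both the injection number and which of the three products was injected there.

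**The concern.** The assessor blind protects both secondary outcomes in section 9.2.2: epidermal thickness (OCT or histology) and KRT9. These are the trial's only evidence of effect. The 4.1.1 exception breaks that blind for the assessors themselves, on a trigger that an itch or a bruise would meet.

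The loss is not random. It falls on participants whose skin reacts. Induration shows the link: section 6.1.1 lists it as a possible reaction, and section 5.2.5 uses measured induration as an alternative to imaged thickness. A responding site could therefore itself be recorded as an adverse event. Thickness readings and adverse-event review take place at the same monitoring visits, and further readings follow up to Day 182. An assessor who has learned the code would take those later readings knowing which site is volar.

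The early-removal rule and the tube labels are two further routes by which identity can reach people who are meant not to have it.

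**Working it through.** The plan gives no figure for code breaks, so there is none to reproduce. The three routes can be set out and sized.

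**Route 1: adverse-event code break**

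Inputs: 20 Phase One participants and up to 100 in all (section 4.1); local reactions in under 10% of participants (section 6.1.1). The true rate below that ceiling is unknown, so 1% and 5% are shown as assumptions.

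Expected participants opened = N × p. Chance of at least one = 1 − (1 − p)^N, treating participants as independent.

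| p | Expected, N = 20 | Chance of at least one, N = 20 | Expected, N = 100 |
|---|---|---|---|
| 1% (assumed) | 20 × 0.01 = 0.2 | 1 − 0.99^20 = 18% | 1 |
| 5% (assumed) | 20 × 0.05 = 1 | 1 − 0.95^20 = 64% | 5 |
| 10% (ceiling) | 20 × 0.10 = 2 | 1 − 0.90^20 = 88% | 10 |

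The last column is generous. Section 4.1 counts people consented, and those who fail screening or whose cells do not expand are never injected, so they have no code to break. In the other direction, adverse events other than local reactions also trigger the exception, and the documents give no rate for them.

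**Route 2: early removal**

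1. The rule asks whether the volar site, and neither other site, is raised. It cannot be applied to numbered readings without the code.
2. Neither 5.2.5 nor 9.2 says who applies it or how the answer is kept from the assessors.
3. Staff who saw one numbered site thicken, and then see removal, can infer that this site is volar. This reaches up to 3 subjects: 3/20 = 15% of Phase One, or 3/100 = 3% overall. It would be 6 of 100 if the footnote repeated in the Phase Two schedule means three per phase.
4. No OCT follows removal, so in these subjects only histology and KRT9 reading can be affected, and only if laboratory staff know the OCT result.
5. While fewer than three subjects have been removed, the reverse inference is open. If a subject has one clearly raised site and is not removed, that site is probably not volar, and that subject is still being measured.

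**Route 3: tube labels**

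Section 4.1.1 labels sites and biopsies by number in place of identity. Appendix VII puts number and identity on the same tube. Both cannot be followed. Under Appendix VII as written, every excised specimen from every participant reaches the laboratory with its identity showing.

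**The case against.** **It is a feasibility study.** The trial is open-label Phase I and its primary outcome is tolerability, which this assessor blind does not protect. That stands, and it limits the harm to the secondary outcomes.

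**The blind fails for both secondary outcomes.** A reader might infer this from the code-break and early-removal rules. The documents do not support it: each rule opens individual participants, and for OCT the blind is weakened, not shown to fail. Only the tube label reaches every participant, and it concerns laboratory samples alone.

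**Early removal biases later OCT.** Not in the removed subjects, who have no later OCT. The leak is also an inference, not a stated disclosure.

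**One break reveals the whole trial.** This would follow if numbers were matched to cell type in one fixed order. Section 4.1.1 describes no randomisation of numbers, but it states no fixed order either.

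**The code break serves no safety purpose.** This goes too far. The clinicians already hold the code, but section 5.2.4 sends a subject with discomfort to any study team member, who need not be the injector. Some need-to-know access is reasonable.

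**A much larger share will be unblinded by events of any kind.** The documents give no overall rate. The collection period is itself unclear: section 7.4.1 ends it 30 days after the last dose, while later visits still list adverse-event assessment.

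**The form may reveal little.** The Appendix V sheet has no volar/non-volar column. Section 4.1.1 nevertheless describes the form as recording the identity of the cells at each number.

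**RT-PCR is less open to judgement** than OCT measurement or histology reading. That is fair; the mechanism is weakest there.

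**Conclusion.** The concern holds in limited form. As written, section 4.1.1 gives the OCT and laboratory assessors access to the code for any adverse event, mild ones included. This erodes their blind participant by participant, in relation to skin reaction. The expected reach through local reactions is at most about 2 of 20 in Phase One and 10 of up to 100 overall, resting on section 6.1.1's ceiling; other events add an unknown number.

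Early removal adds a possible inference in up to three subjects, confined to tissue reading and conditional on the laboratory knowing the OCT result. It also gives a weaker hint in subjects who have a raised site and stay in follow-up.

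Appendix VII contradicts section 4.1.1 outright for all laboratory samples. The three routes together call for an amendment to protect the secondary outcomes. They do not touch the primary outcome.

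**What to change.** 1. **Section 4.1.1.** Replace the adverse-event exception with a rule that the code is opened only to those managing the event who need the identity, that OCT, histology and KRT9 assessors stay blinded through adverse events, and that any opening to an assessor is logged with date and reason.
2. **Sections 5.2.5 and 9.2.** State that the unblinded clinician, not the OCT staff, applies the early-removal rule to the numbered readings. This does not stop OCT staff guessing when a subject with a raised site returns, but it keeps the formal result from them.
3. **Appendix VII.** Remove identity from the tube label and give each specimen a fresh code unrelated to site numbers 1 to 3, with the list held by the clinician. Do not tell the laboratory whether removal was early or scheduled. Re-coding under 4.1.1 alone would achieve nothing while Appendix VII still prints the identity.

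The cost is a few sentences in the protocol and one more code list to keep. Participants undergo no additional procedures.
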